#### 7.3.1.4. Anthropometric Parameters

Anthropometric indicators of growth will be plotted on standard growth curves. Z-scores and percentiles based on the age-gender standardized norms will be calculated in accordance with the methodology described by the WHO (subjects  $\leq 24$  months) or CDC (subjects > 24 months to 18 years) and using the growth charts relevant to the respective methodology. Summaries will include summaries of observed z-scores and percentiles at each visit and also the change from baseline and the percentage change from baseline (percentile data only). In addition, the percentages of subjects who meet criteria for underweight (<-2 standard deviations [SD] from the median for WFA), stunting (<-2 SD from the median for LFA/HFA), and wasting (<-2 SD from the median for WFL/WFH) will be tabulated for each time point.

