3.2.2.2 Efficacy

The study is designed to confirm the efficacy of treatment with sebelipase alfa in subjects with rapidly progressive disease presenting in infancy. Survival endpoints will include proportion of subjects surviving to 12, 18, and 24 months of age, and other timepoints, as data permit, and estimated median age at death. Survival rates and median age at death derived from this study will be compared to rates/times reported in the literature and previous studies.

Subjects with LAL Deficiency presenting in infancy typically stop growing and this growth failure, in addition to being the predominant clinical feature, is also one of the main contributors to mortality. Improvement in growth is anticipated to be a prerequisite for any beneficial effects of sebelipase alfa on survival. Therefore, efficacy endpoints will include changes from baseline in the following growth parameters:

- Percentiles and/or z-scores, based on WHO child growth standards (WHO Multicentre Growth Reference Study Group, 2006 and 2007), for the following parameters:
 - Weight-for-age (WFA)
 - o WFL or WFH
 - LFA or HFA
 - Head circumference-for-age (HCFA)
 - Mid-upper arm circumference-for-age (MUACFA)
- Dichotomous growth status indicators for underweight, wasting, and stunting based on WFA, WFL/WFH, and LFA/HFA, respectively (UNICEF, 2009)

Note: Given the switch at age 2 years from measurement of length to measurement of height, growth parameters include weight related to both length and height and age related to both length and height.

A successful therapy for LAL Deficiency presenting in infancy should also mitigate the liver and hematological changes associated with the disease. Therefore, the following laboratory parameters will also be included as efficacy endpoints:

- Changes from baseline in aspartate aminotransferase [AST] and ALT levels
- Normalization of hemoglobin levels without requirement for blood transfusion
- Changes from baseline in serum ferritin levels

Additional exploratory efficacy parameters will be investigated to provide supportive evidence of an improvement of LAL Deficiency with sebelipase alfa treatment, and will include changes or percent changes from baseline (or first available assessment if baseline data are unavailable) in:

- Alkaline phosphatase, gamma glutamyltransferase (GGT), albumin, and bilirubin (direct, indirect, and total)
- Liver and spleen size/volume, as measured by ultrasound or magnetic resonance imaging (MRI)

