8.7 Efficacy Analysis

Efficacy will be analyzed for the Full Analysis Set.

Survival will be analyzed as the proportion of subjects surviving to 12, 18, and 24 months of age. As a complementary analysis, Kaplan-Meier survival curves of survival since birth and survival since first dose of IMP will be presented. Median age at death will also be calculated. A Kaplan Meier estimate of median survival past first dose of IMP will be computed.

Estimated survival rates and median age at death derived from this study will be compared to rates/times reported in the literature, and will be discussed in conjunction with information derived from previous studies.

Anthropometric indicators of growth, standardized by age and gender in accordance with the methodology described by the WHO and using WHO growth charts will be listed by study time point as observed values and as changes from baseline. Change from baseline in anthropometric data will be provided as graphs, and also tabulated as continuous data. In addition, the percentages of subjects who meet criteria for underweight, stunting, and wasting will be tabulated for each timepoint.

Change and/or percent changes from baseline in AST, ALT, and serum ferritin will be presented graphically (and tabulated) for each evaluation timepoint.

A subject will be considered to have achieved transfusion-free hemoglobin normalization (TFHN) if the subject meets all of the following criteria:

- 1. Has two post-baseline measurements of hemoglobin at least 4 weeks apart that are both above the age-adjusted lower limit of normal (LLN)
- 2. Has no known additional measurements of hemoglobin that are below the age-adjusted LLN during the (minimum) 4-week period; and
- 3. Had no transfusions during the (minimum) 4-week period, and also no transfusions for 2 weeks prior to the first hemoglobin measurement in the (minimum) 4-week period

If all 3 criteria are met, the subject will be considered to have achieved TFHN on the date of the first hemoglobin assessment in the 4-week period. The proportion of subjects who achieve TFHN will be summarized and, if sufficient data are available, a summary of time to TFHN will be created.

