# 4.1. Changes from Analyses Specified in the Protocol

Protocol Section 4.5 defines a concomitant medication as a medication starting or ongoing at the time of the signing of the informed consent. However, concomitant medications will be defined relative to the first dose of sebelipase alpha.

In the protocol, an exploratory objective is to evaluate potential disease-related biomarkers. Biomarker samples are stored for future analysis and will not be analyzed for this analysis plan.

The protocol mentions pharmacokinetic analysis is a secondary objective and will be done by IV infusion. PK analysis will not be analyzed as part of this analysis plan.

No formal inferential statistical testing will be performed.

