## 5.2. Efficacy

#### 5.2.1. Secondary Endpoint(s)

Efficacy endpoints will include the following:

- Proportion of subjects surviving to 12, 18, 24, and 36 months of age, and other time points, as data permit
- Median age at death
- The change from baseline in percentiles and z-scores, based on World Health Organization (WHO) child growth standards (WHO Multicentre Growth Reference Study Group, 2006 and 2007), for the following parameters:
  - Weight-for-age (WFA)
  - Weight-for-length (WFL) or Weight-for-height (WFH)
  - Length-for-age (LFA) or Height-for-age (HFA)
  - Head circumference-for-age (HCFA)
  - Mid-upper arm circumference-for-age (MUACFA)
- Dichotomous growth status indicators for underweight, wasting, and stunting based on WFA, WFL/WFH, and LFA/HFA, respectively (UNICEF, 2009)
- Change from baseline in Aspartate Aminotransferase (AST) and Alanine Aminotransferase (ALT) levels
- Normalization of hemoglobin levels without requirement for blood transfusion
- Changes from baseline in serum ferritin levels
- Change in Total and function area scores on the Denver II Development Screening Test (DDST)
- Biomarker samples will be stored for future analysis as required. Biomarkers will not be analyzed for this report.

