#### 7.3.1.2. Abdominal Magnetic Resonance or Abdominal Ultrasound

Change and percent change in liver and spleen volume in multiples of normal and fat content will be calculated from Baseline and tabulated for each evaluation time point. Multiples of normal are defined in Section 9.4.10. Change from baseline will only be calculated if the same mode of assessment, MRI or ultrasound, was used at baseline and post-baseline. Data will be summarized for the endpoints as continuous variables.

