#### 9.4.12.2 Z-Scores in Growth Curves

Alternatively, the formula for the Z-score can also be expressed as:

$$Z = \frac{\left[\frac{observed \ value}{M}\right]^{L} - 1}{L * S}; \qquad whenever \ L \neq 0$$

$$Z = \frac{\log_e\left(\frac{observed value}{M}\right)}{S}; \quad whenever L = 0$$

where L (lambda: power in Box-Cox transformation, reflecting degree of skewness), M (mu: the median) and S (sigma: the generalized coefficient of variation) are curve parameters – which vary according to the child's sex and age (e.g. weight-for-age among boys) or according to the child's sex and height (e.g. weight-for-height among boys) – determined from smoothed percentile curves using a series of linear and non-linear regression models and a modified LMS procedure *(Cole TJ, Freeman JV, Preece MA. British 1990 growth reference centiles for weight,* 

Alexion Pharmaceuticals LAL-CL08

*height, body mass index and head circumference fitted by maximum penalized likelihood. Stat Med. 1998;17:407–429).* 

The estimates of L, S and M have been tabulated - for different anthropometric parameters - for a series of ages by WHO and CDC using datasets from surveys conducted in the United States. The estimates for these parameters are available from publicly available WHO Growth Charts (for patients  $\leq$ 24 months of age) and CDC Growth Charts (subjects >24 months of age to 18 years) and can be used to calculate Z-scores and percentiles for observed anthropometric parameters.

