#### 9.4.12.5 Note on Z Scores and Percentiles

1. Will only be calculated for patients  $\leq 18$  years at informed consent

- For Subjects ≤24 months of age, z-scores and percentile scores based on World Health Organization (WHO) growth charts (WHO Multicentre Growth Reference Study Group, 2006 and 2007)
- 3. For subjects >24 months of age to 18 years, z-scores and percentile scores based on Centers for Disease Control and Prevention (CDC) growth charts (Kuczmarski et al., 2000)

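### The SAP scores growth on WHO charts to 24 months of age and CDC charts afterwards, against the protocol's WHO-only definition, so later changes from baseline mix two references

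*SAP*

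**What the plan says.** **WHO only.** Protocol 8.7 standardises growth "in accordance with the methodology described by the WHO and using WHO growth charts". Protocol 3.2.2.2 and 5.1.5 also name WHO standards alone, for all five indices: weight-for-age, weight-for-length/height, length/height-for-age, head circumference and mid-upper arm circumference. None of these sections gives an upper age. SAP 5.2.1 agrees, defining the secondary endpoint as "The change from baseline in percentiles and z-scores, based on World Health Organization (WHO) child growth standards".

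**WHO, then CDC.** SAP 7.3.1.4 uses WHO to 24 months and then "CDC (subjects > 24 months to 18 years) and using the growth charts relevant to the respective methodology". SAP 9.4.12.2 takes the later curve parameters from "CDC Growth Charts (subjects >24 months of age to 18 years", and SAP 9.4.12.5 repeats the rule for that age group: "z-scores and percentile scores based on Centers for Disease Control and Prevention (CDC) growth charts".

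**The list of departures.** SAP 4.1, headed "Changes from Analyses Specified in the Protocol", covers the concomitant-medication definition, biomarkers, PK and the absence of inferential testing. The growth reference is not there.

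**What is tabulated.** SAP 7.3.1.4 plans observed z-scores and percentiles by visit, their change from baseline, percent change from baseline for percentiles, and the proportions below -2 SD for underweight, stunting and wasting.

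**The concern.** Growth is a stated secondary objective, and the SAP changes its yardstick partway through follow-up without declaring it. The SAP contradicts both the protocol and its own endpoint definition.

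The consequence goes beyond documentation. A z-score states a position relative to a reference population. Subtracting a baseline scored on one reference from a later value scored on another yields a growth change plus whatever the two references differ by, and the table cannot separate them. The -2 SD indicators likewise refer to a different population after 24 months, so a child near the cut-off could change category with no change in growth.

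The SAP recognises this kind of problem elsewhere. For liver and spleen, "Change from baseline will only be calculated if the same mode of assessment, MRI or ultrasound, was used at baseline and post-baseline". Growth has no equivalent rule.

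A smaller, separate point is that percent change in a percentile divides by a number close to zero in children with growth failure, who are among those this study expects to enrol.

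**Working it through.** The documents state no figure for this point that could be reproduced. The check is a comparison of the text, followed by age arithmetic.

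**Inputs**
- Age at first dose: 0 to 8 months (Protocol 4.4 excludes children older than 8 months at first dosing).
- Baseline: last assessment before the first infusion (SAP 9.4.8.1).
- Treatment: expected to last at least 18 months, up to 3 years (Protocol 3.2.3).
- Change of reference: 24 months of age (SAP 7.3.1.4).
- Subjects: at most 10 (Protocol 4.2, SAP 9.3).

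**Step 1: which reference applies to baseline.** Baseline precedes a first dose given at 8 months of age or younger, so every baseline is scored on WHO. Every change from baseline after 24 months of age is therefore CDC minus WHO.

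**Step 2: how much follow-up is affected.** Months after age 24 months = max(0, age at first dose + treatment months - 24).

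| Treatment | First dose at 0 months | First dose at 8 months | Share of treatment time |
|---|---|---|---|
| 18 months | max(0, 0 + 18 - 24) = 0 | 8 + 18 - 24 = 2 | 0/18 to 2/18 = 0% to 11% |
| 24 months | 0 + 24 - 24 = 0 | 8 + 24 - 24 = 8 | 0/24 to 8/24 = 0% to 33% |
| 36 months | 0 + 36 - 24 = 12 | 8 + 36 - 24 = 20 | 12/36 to 20/36 = 33% to 56% |

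With 18 months of treatment, only children first dosed after 6 months of age cross the line.

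**Step 3: where it falls in tables by study week.** One month is 365.25/12/7 = 4.348 weeks. A child first dosed at birth crosses at 24 × 4.348 = Week 104.4, and one first dosed at 8 months crosses at 16 × 4.348 = Week 69.6. The spread is about 35 weeks, so one visit row can combine WHO-scored and CDC-scored children. Of the 13 twelve-weekly time points from Week 12 to Week 156, 5 to 8 fall after 24 months of age.

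**Step 4: the growth-status rates.** One child is 1/10 = 10 percentage points with 10 subjects, and more with fewer.

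**Step 5: percent change in percentiles.** Percentile P = 100 × Φ(z): z = -3 gives 0.135, -2 gives 2.275, -1 gives 15.866 and 0 gives 50. Percent change = 100 × (P_post/P_base - 1).
- z from -1 to 0: +215%
- z from -2 to -1: +597%
- z from -3 to -1: +11,653%

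The first two are the same gain of one SD. As an illustration on assumed data, take nine children going from -1 to 0 and one from -3 to -1. The mean is (9 × 215.1 + 11,653.1)/10 = +1,359%, while the median is +215%.

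**The case against.** The CDC rule is prespecified, appears consistently in three places and has its source cited. It is a deliberate choice, and Protocol 8.1 leaves methodological detail to the SAP. That is fair, but a deliberate change to how a secondary endpoint is scored belongs in SAP 4.1. Listing it there would cure the documentation fault and still leave CDC-minus-WHO changes in the tables.

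The size of the effect is unknown. This stands: the documents give no L, M or S values, so neither size nor direction can be computed. The 10-point figure shows how sensitive the rates are; it is not evidence that any child would be reclassified.

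Exposure is smaller for two indices. This also stands. Appendix A stops the three-monthly head and mid-upper arm circumference measurements at Week 96, about 22.1 months after first dose. Those measurements can run at most about 6 months past age 24 months, and not past it at all if first dose is before about 1.9 months of age. The 33% to 56% share concerns the weight and length/height indices.

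SAP 9.4.12.3 sets the malnutrition cut-offs against an international reference, which could be read as keeping one reference for those indicators. That reading conflicts with the CDC rule for z-scores in the same appendix, so it is a further inconsistency to resolve.

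A break at age 2 exists anyway. Protocol 3.2.2.2 acknowledges it ("Given the switch at age 2 years from measurement of length to measurement of height") and handles it by pairing length-based with height-based indices under WHO. Using WHO throughout does not remove that break, but it avoids adding a second one.

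On percentiles, the SAP also reports medians, quartiles and change in z-score, so the distortion is mainly in the mean. That makes the point minor, but the summary adds nothing reliable and Protocol 8.7 does not plan it.

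**Conclusion.** The concern holds. The SAP replaces the protocol's growth reference after 24 months of age, contradicts its own 5.2.1 and does not declare the change. Every later change from baseline mixes references. Under a full 36 months of treatment this covers 33% to 56% of treatment time for the weight and length/height indices; under 18 months it covers 0% to 11%. These ranges assume first dose anywhere from birth to 8 months of age.

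The importance is moderate. The analyses are descriptive, no error rate or sample size depends on this, and visits up to 24 months of age, including everything in the 12-month report, are unaffected. The shift may be small, but its size is unknown and the planned tables would not reveal it. It should be corrected before the final analysis.

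**What to change.** 1. In SAP 7.3.1.4, 9.4.12.2 and 9.4.12.5, use WHO standards at all ages in this study for every z-score, percentile and growth-status indicator, with length-based tables to 24 months and height-based tables afterwards.
2. In SAP 9.4.12.3, name WHO as the reference for the cut-offs.
3. If CDC values are wanted, present them as supplementary, score baseline on the same chart, and list the addition with its reason in SAP 4.1.
4. Delete percent change from baseline in percentiles and rely on the change in z-score already planned. Because SAP 7.3 applies percent change to continuous endpoints by default, state in 7.3.1.4 that none is calculated for growth scores.

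The cost is SAP wording and a change of lookup table. No new data are needed, and the protocol's definition is restored.

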# 7. STATISTICAL ANALYSIS

The Alexion Biostatistics Department or designee will perform the statistical analysis of the data derived from this trial. The analysis will be performed using the SAS® Life Science Analytics Framework version 4.7.2 or higher.

No formal inferential statistical testing will be performed. As appropriate, 95% two-sided confidence intervals (CIs) will be calculated around the estimates based on the exact binomial distribution (Clopper-Pearson method) for binomial endpoints and the t-distribution for continuous endpoints. Confidence intervals, where presented, will be considered descriptive and will be provided to facilitate clinical review and interpretation.

All data collected in this study will be provided in subject data listings sorted by subject number; the dose of SBC-102 temporally associated with the data will be included on the listing. Summary tables and/or graphs will be presented for each endpoint, as appropriate to the data, by evaluation time point.

Unless otherwise noted, the following standard conventions will be used for creating descriptive summaries:

- Continuous numeric endpoints will be summarized by providing the number of subjects with non-missing data, the mean and standard deviation (SD) of the data, and the minimum, first quartile (Q1), median, third quartile (Q3), and maximum value. Mean, median values, Q1 and Q3 will be presented with one decimal point more than the original value, SD will be displayed with two decimal points more than the original value will have the same number of decimal points as the original value;
- For categorical endpoints, the number and percentage of subjects with each possible outcome will be displayed. The denominator for percentages will include subjects with missing data.

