# 7.3. Efficacy Analyses

Efficacy will be examined on the FAS. For the continuous endpoints, the observed values, change from baseline and percent change from baseline at each time of assessment will be summarized, and may include 95% confidence intervals (e.g. for time points with  $\geq 2$  observed data points).

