#### 9.4.8.3 Percent Change from Baseline

Percent change from baseline will be calculated as:

Percent Change of Baseline = [(Assessment Value – Baseline Assessment Value)/(Baseline Assessment Value)]\*100 and rounded to 2 decimal places.

Similarly, the percent change from pre-infusion, at a given visit, will be calculated as the infusion or post-infusion value minus the pre-infusion value, all divided by the pre-infusion value.

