## 9.4.12.4 Percentiles

Percentiles are cumulative probabilities associated with z-scores using Standard Normal distribution theory. Z-scores, by definition, have a Standard Normal Distribution.

Source: Pierce, Rod. (11 Oct 2014). "Normal Distribution". Math Is Fun. Retrieved 14 Jan 2016 from http://www.mathsisfun.com/data/standard-normal-distribution.html

For example, a z-score of +2 would be equal to the 97.7 percentile on the standard normal curve, meaning the patient's Z-score is in the top 2.3% in comparison to his/her reference population.

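### SAP 7.3.1.4 includes percentage change in growth percentiles; dividing by a very low baseline lets one child reverse the sign of the cohort mean

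*SAP*

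**What the plan says.** SAP 7.3.1.4 plans growth-curve plots, observed z-scores and percentiles at each visit, "also the change from baseline and the percentage change from baseline (percentile data only"), and the rates of underweight, stunting and wasting. The reference is WHO up to 24 months of age and CDC after that.

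Three other SAP rules determine what the percentage change will be:

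- SAP 9.4.12.4 defines the scale: "Percentiles are cumulative probabilities associated with z-scores using Standard Normal distribution theory".
- SAP 9.4.8.3, which opens "Percent change from baseline will be calculated as", gives the difference divided by the child's own baseline value, times 100. It has no rule for a zero or near-zero baseline.
- SAP 7 summarizes continuous endpoints by "the mean and standard deviation (SD) of the data, and the minimum, first quartile (Q1), median, third quartile (Q3), and maximum value", so the mean is a planned output.

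SAP 7.3 also has a general rule: "For the continuous endpoints, the observed values, change from baseline and percent change from baseline at each time of assessment will be summarized". It adds that 95% confidence intervals may be given.

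The growth endpoint in SAP 5.2.1 is change from baseline in percentiles and z-scores; percentage change is not part of it. Protocol 8.7 says of growth: "Change from baseline in anthropometric data will be provided as graphs, and also tabulated as continuous data". The same section allows change or percent change for AST, ALT and ferritin.

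**The concern.** A percentile lies between 0 and 100 and is strongly compressed in the lower tail. A ratio to a baseline in that tail mostly measures how low the child started, not how much the child grew. The ratio is also lopsided: a loss cannot go beyond −100%, while a gain from a tiny baseline has no practical limit.

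Very low baselines are plausible in some children, because weight-for-height at least 2 SD under the mean is one of the possible entry signs (Protocol 4.3). Higher baselines are plausible in others, because growth failure is not an entry requirement (Protocol 3.2.2.1). That mixture is where the mean of such ratios behaves worst.

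Growth is a secondary objective, and Protocol 3.2.2.2 expects better growth to precede any survival benefit. The study has at most 10 children, no control group and no hypothesis test, so its descriptive tables are the evidence. A column whose mean can contradict the z-score change beside it could be quoted on its own.

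**Working it through.** **Inputs.** The percentile definition is from SAP 9.4.12.4, the percent-change formula from SAP 9.4.8.3, the use of the mean from SAP 7, and the maximum of 10 children from Protocol 4.2 and SAP 9.3. All individual z values below are assumptions.

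**Formulas.** Percentile P(z) = 100 × Φ(z). Percentage change = 100 × (P(post) − P(baseline)) / P(baseline).

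**Step 1: the SAP's own figure.** The SAP states that "a z-score of +2 would be equal to the 97.7 percentile on the standard normal curve". 100 × Φ(2) = 97.72, with 2.28 above it, so the figure reproduces.

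**Step 2: one and the same gain of 1 z from different baselines.**

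| Baseline z | Baseline percentile | Percentile after +1 z | Percentage change |
|---|---|---|---|
| −4 | 0.0032 | 0.135 | +4,162% |
| −3 | 0.135 | 2.28 | +1,585% |
| −2 | 2.28 | 15.87 | +597% |
| −1 | 15.87 | 50 | +215% |
| 0 | 50 | 84.13 | +68% |

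**Step 3: cohorts of 10.** Let nine children fall from z −1.0 to −1.5. Each goes from percentile 15.87 to 6.68, a change of −57.89%. Together they contribute 9 × (−57.89) = −521.0.

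- Tenth child from −2 to −1: (597.4 − 521.0) / 10 = **+7.6%**.
- Tenth child from −3 to −2: (1,585.3 − 521.0) / 10 = **+106.4%**.
- In both, mean z change = (1 − 9 × 0.5) / 10 = **−0.35**, and the median percentage change is −57.9%.

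With these nine children, any single value above about +521% makes the mean positive.

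**Step 4: the optional interval.** In the +106.4% cohort the SD is 519.6. With t(9) = 2.262, the half-width is 2.262 × 519.6 / √10 = 371.7, so the 95% interval runs from −265% to +478%. The lower limit is impossible, since no percentile can fall by more than 100%.

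**Step 5: a more extreme assumed cohort.** One child rises from z −4 to −2 (+71,732%). Nine children each lose 1 z: three from −2 (−94.07%), four from −1 (−85.66%) and two from 0 (−68.27%).

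- Sum of the losses: −282.2 − 342.6 − 136.5 = −761.4, with rounding.
- Mean: (71,732 − 761) / 10 = **+7,097%**; median −86%.
- Mean z change: (2 − 9) / 10 = **−0.7**.

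**Step 6: z-scores under the general rule.** Percentage change fails on z-scores too, because a negative baseline reverses the sign. An improvement from −3 to −1 gives 100 × 2 / (−3) = −67%.

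**The case against.** The strongest reply is that this is one descriptive column among several. Change in z-score, change in percentile, medians, quartiles, extremes and by-subject listings are all planned. In every cohort above, the mean z change and the median percentage change show the loss. Confidence intervals are optional, nothing is tested, and no decision depends on the figure. All of this stands, and it limits the weight of the point. The rate below −2 SD is a weaker safeguard: it goes from 1 to 3 of 10 in the Step 5 cohort, but from 1 to 0 of 10 when the tenth child moves from −3 to −2.

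Four stronger readings are tempting, and the documents do not support them:

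- *Growth is reported mainly as percentage change in percentile.* It is an added summary and is not the listed endpoint.
- *Nearly all baselines will be under the 2.3rd percentile.* No baseline growth data are given, and a low weight-for-height is only one of several possible entry signs.
- *The sickest child will drop out because the baseline percentile is zero.* If percentiles were stored to one decimal, z of about −3.3 or lower would become 0.0 and the ratio would be undefined. The SAP does not say that they are; SAP 9.4.8.3 rounds only the resulting percent change.
- *The column contradicts the protocol.* Protocol 8.1 leaves analysis details to the SAP, so the column is an addition that the protocol does not call for.

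**Conclusion.** The percentage-change item is wrong as written. By the SAP's own definitions, its mean can have the opposite sign to the mean z-score change in a cohort of at most 10. This does not need an extreme case: one child gaining 1 z from −2, against nine each losing 0.5 z from −1, is enough (+8% against −0.35). From −3 the same gain gives +106%, and the Step 5 cohort gives +7,097% against −0.7.

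These sizes rest on assumed z values. The distortion arises only if a child with a very low baseline improves, so it is a possibility and not a forecast. The mechanism needs no assumption beyond the two SAP formulas. Absolute change in percentile is not faulted here.

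**What to change.** 1. In SAP 7.3.1.4, in the sentence containing "also the change from baseline and the percentage change from baseline (percentile data only"), delete the percentage-change part and keep the change from baseline.
2. In SAP 7.3, state that the general percent-change summary does not apply to growth z-scores or percentiles, and that change in z-score is the leading growth measure. The exclusion is needed because, once the percentile-only restriction in 7.3.1.4 is gone, the general rule would otherwise cover both scales.

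Keep observed percentiles and absolute change in percentile, which is part of the endpoint listed in SAP 5.2.1. The cost is two short SAP edits and one fewer table column. No new data are needed, and nothing interpretable is lost because change in z-score is already planned.
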